Appendix IV
EORTC QLQ - C30 (Version 3)

We are interested in some things about you and your health. Please answer all of the questions yourself by circling the number that best applies to you. There are no "right" or "wrong" answers. The information that you provide will remain strictly confidential.

	Not at All	A Little	Quite a Bit	Very Much
1. Do you have any trouble doing strenuous activities, like carrying a heavy shopping bag or a suitcase?	1	2	3	4
2. Do you have any trouble taking a long walk?	1	2	3	4
3. Do you have any trouble taking a short walk outside of the house?	1	2	3	4
4. Do you need to stay in bed or a chair during the day?	1	2	3	4
5. Do you need help with eating, dressing, washing yourself or using the toilet?	1	2	3	4

During the past week:

	Not at All	A Little	Quite a Bit	Very Much
6. Were you limited in doing either your work or other daily activities?	1	2	3	4
7. Were you limited in pursuing your hobbies or other leisure time activities?	1	2	3	4
8. Were you short of breath?	1	2	3	4
9. Have you had pain?	1	2	3	4
10. Did you need to rest?	1	2	3	4
11. Have you had trouble sleeping?	1	2	3	4
12. Have you felt weak?	1	2	3	4
13. Have you lacked appetite?	1	2	3	4
14. Have you felt nauseated?	1	2	3	4
15. Have you vomited?	1	2	3	4

During the past week:

	Not at All	A Little	Quite a Bit	Very Much
16. Have you been constipated?	1	2	3	4
17. Have you had diarrhea?	1	2	3	4
18. Were you tired?	1	2	3	4

19. Did pain interfere with your daily activities?	1	2	3	4
20. Have you had difficulty in concentrating on things, like reading a newspaper or watching television?	1	2	3	4
21. Did you feel tense?	1	2	3	4
22. Did you worry?	1	2	3	4
23. Did you feel irritable?	1	2	3	4
24. Did you feel depressed?	1	2	3	4
25. Have you had difficulty remembering things?	1	2	3	4
26. Has your physical condition or medical treatment interfered with your family life?	1	2	3	4
27. Has your physical condition or medical treatment interfered with your social activities?	1	2	3	4
28. Has your physical condition or medical treatment caused you financial difficulties?	1	2	3	4

For the following questions please circle the number between 1 and 7 that best applies to you.

29. How would you rate your overall health during the past week?

1	2	3	4	5	6	7
Very poor						Excellent

30. How would you rate your overall quality of life during the past week?

1	2	3	4	5	6	7
Very poor						Excellent

Appendix V EORTC QLQ – BIL21

Patients sometimes report that they have the following symptoms or problems. Please indicate the extent to which you have experienced these symptoms or problems during the past week. Please answer by circling the number that best applies to you.

During the past week:	Not at All	A Little	Quite a Bit	Very Much
31. Have you had trouble with eating?	1	2	3	4
32. Have you felt full up too quickly after beginning to eat?	1	2	3	4
33. Have you had problems with your sense of taste?	1	2	3	4
34. Were you restricted in the types of food you can eat as a result of your disease or treatment?	1	2	3	4
35. Have your skin or eyes been yellow (jaundiced)?	1	2	3	4
36. Have you had itching?	1	2	3	4
37. Have you been worried about your skin being yellow?	1	2	3	4
38. Have you been less active than you would like to be?	1	2	3	4
39. Have you felt 'slowed down'?	1	2	3	4
40. Have you felt lacking energy?	1	2	3	4
41. Did you have pain during the night?	1	2	3	4
42. Have you had pain in your stomach area?	1	2	3	4
43. Have you had pain in your back?	1	2	3	4
44. Did you have a bloated feeling in your abdomen?	1	2	3	4
45. Have you felt stressed?	1	2	3	4
46. Have you felt less able to enjoy yourself?	1	2	3	4
47. Have you worried about your health in the future?	1	2	3	4
48. Have you worried about your family in the future?	1	2	3	4
49. To what extent have you been troubled with side effects from your treatment?	1	2	3	4
50. Have you had difficulties with drainage tubes/bags?	1	2	3	4
51. Have you worried about losing weight?	1	2	3	4

Appendix VI SKINDEX-16

Directions: Please circle the number (0-6) best reflecting your response to the following that describes during the past week, how often have you been bothered by:

1. Your skin itching:

0	1	2	3	4	5	6	7	8	9	10
Never bothered									Always bothered	

2. Your skin burning or stinging:

0	1	2	3	4	5	6	7	8	9	10
Never bothered									Always bothered	

3. Your skin hurting:

0	1	2	3	4	5	6	7	8	9	10
Never bothered									Always bothered	

4. Your skin being irritated:

0	1	2	3	4	5	6	7	8	9	10
Never bothered									Always bothered	

5. The persistence/recurrence of your skin condition:

0	1	2	3	4	5	6	7	8	9	10
Never bothered									Always bothered	

6. Worry about your skin condition (for example, that it will spread, get worse, scar or be unpredictable, etc.):

0	1	2	3	4	5	6	7	8	9	10
Never bothered									Always bothered	

7. The appearance of your skin:

0	1	2	3	4	5	6	7	8	9	10
Never bothered									Always bothered	

8. Frustration about your skin:

0	1	2	3	4	5	6	7	8	9	10
Never bothered										Always bothered

9. Embarrassment about your skin:

0	1	2	3	4	5	6	7	8	9	10
Never bothered										Always bothered

10. Being annoyed about your skin:

0	1	2	3	4	5	6	7	8	9	10
Never bothered										Always bothered

11. Feeling depressed about your skin:

0	1	2	3	4	5	6	7	8	9	10
Never bothered										Always bothered

12. The effects of your skin on your interactions with others (for example, interactions with family, friends, close relationship, etc.):

0	1	2	3	4	5	6	7	8	9	10
Never bothered										Always bothered

13. The effects of your skin on your desire to be with people:

0	1	2	3	4	5	6	7	8	9	10
Never bothered										Always bothered

14. Your skin making it hard for you to show your affection:

0	1	2	3	4	5	6	7	8	9	10
Never bothered										Always bothered

15. The effects of your skin condition on your daily activities:

0	1	2	3	4	5	6	7	8	9	10
Never bothered										Always bothered

16. Your skin making it hard to work or do what you enjoy:

0 1 2 3 4 5 6 7 8 9 10
Never bothered Always bothered

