2.32 Assess preliminary evaluation of FGFR2 pathway perturbation with ponatinib

2.33 To describe patient-reported health-related quality of life and symptoms

3.0 Patient Eligibility

3.1 Inclusion Criteria

3.11 Age \geq 18 years

3.12 Histological/cytological confirmation of biliary cancer.

3.13 Confirmation of advanced biliary cancer that is refractory or intolerant to gemcitabine or fluoropyrimidine based therapy with FGFR2 fusion [using Next-Gen sequencing assays (such as Foundation One®) or fluorescent in situ hybridization (FISH) break-apart assays] or FGFR pathway mutation/amplification [using Next-Gen sequencing assays (such as Foundation One®)]. Assays must be performed in a CLIA certified laboratory and done as a CLIA validated test or RUO in a CLIA laboratory.

3.14 Measurable disease as defined in Section 11.0.

3.15 ECOG Performance Status (PS) 0, 1 or 2 (Appendix I).

- 3.16 The following laboratory values obtained ≤ 14 days prior to registration.
- Absolute neutrophil count (ANC) $\geq 1500/\text{mm}^3$
 - Platelet count $\geq 100,000/\text{mm}^3$
 - Hemoglobin ≥ 9.0 g/dL
 - Total bilirubin ≤ 1.5 x upper limit of normal (ULN), unless due to Gilbert's syndrome
 - Aspartate transaminase (AST) and Alanine Aminotransferase (ALT) < 3 x ULN
 - Creatinine ≤ 1.5 x upper limit of normal (ULN)
 - Serum lipase and amylase ≤ 2.5 x upper limit of normal (ULN). Note: If subject has tumor involvement in the liver ≤ 3 x ULN.
- 3.17 Negative pregnancy test done ≤ 7 days prior to registration, for women of childbearing potential only.
- 3.18 Recovered from prior radiotherapy and/or systemic therapy related toxicities to Grade ≤ 1
- 3.19a Provide informed written consent.
- 3.19b Life expectancy ≥ 3 months
- 3.19c Willing to return to enrolling institution for follow-up (during the Active Monitoring Phase of the study).
- Note: During the **Active Monitoring** Phase of a study (i.e., active treatment and observation), participants must be willing to return to the consenting institution for follow-up.*
- 3.19d Female and male patients who are fertile agree to use an effective form of contraception with their sexual partners from registration through 4 months after the end of treatment.
- 3.19e Ability to complete questionnaire(s) by themselves or with assistance.

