16.34 Analysis of Patient-Reported Outcomes (Quality of Life and Symptoms)

Patient-reported outcomes (quality of life and symptoms) will be assessed prior to review of treatment response and discussions of patient's general health since last treatment evaluation. Patient-reported outcomes will include the EORTC QLQ-C30, a 30-item patient-reported questionnaire about patient ability to function, symptoms related to the cancer and its treatment, overall health and quality of life, and perceived financial impact of the cancer and its treatment. 28 of the 30 items are measured on a 1-4 scale (1=not at all; 4=very much) with the remaining two items (overall health and overall quality of life) scored on a 1-7 numeric analogue scale (1=very poor; 7=excellent). The recall period for the EORTC QLQ-C30 is one week. The EORTC QLQ-C30 is the product of more than a decade of collaborative research and to date, more than 2200 studies using the EORTC QLQ-C30 have been registered with the EORTC (Fayers et al, 2001 [EORTC Scoring Manual]). In addition, patients will complete the newly developed EORTC QLQ-BIL21. This EORTC module assessed quality of life domains specific to biliary cancers using 21 items on the same 1-4 scale as the core questionnaire. This questionnaire is in the process of being validated (data from this study may be used to provide validation information). Skin and bowel symptoms will be assessed using the Skindex-16 and Bowel Function Questionnaire (BFQ). The Skindex-16 contains 16 questions each on a 0-10 scale (0=never bothered, 10=always bothered) assessing skins problems and has previously been validated (Chren et al, 2001). The BFQ, developed and created by Mayo Clinic physicians, identifies patient-reported problems with various aspects of bowel function (yes or no response) to help evaluate how bowel dysfunction affects normal activities and quality of life (QOL). Content validity of this instrument has been previously reported (Atherton et al, 2013). We will use the Uniscale assessment of overall quality of life (Sloan, O'Fallon et al, 1998) on a scale of 0-10 (0=as bad as it can be, 10=as good as it can be). This single item is one of the most widely used quality of life measures and has been shown to be prognostic for survival above and beyond performance status and other common prognostic factors in a range of cancer types. The Was It Worth It (WIWI) questionnaire is minimalist and efficient, asking only five key questions with trichotomous responses about the patient's satisfaction with the study and likelihood of recommending it to other patients. This tool has been pilot tested in a recent clinical trial looking at the QOL of patients participating in phase I clinical trials at Mayo Clinic Rochester and has demonstrated to be easy to complete, understandable, and important to patients. It has also been used to assess patient satisfaction as a companion protocol (N0392) to North Central Cancer Treatment Group cancer treatment phase II and III clinical trials.

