
A paper booklet containing all the patient-reported outcomes will be administered in clinic at baseline and every cycle, and each PRO will be scored according to the published scoring algorithm. Scale score trajectories over time will be examined using stream plots and mean plots with standard deviation error bars overall. Changes from baseline at each cycle will be statistically tested using paired t-tests, and standardized response means (mean of the change from

baseline scores at a given cycle, divided by the standard deviation of the change scores) will be interpreted (after applying Middel's (2002) adjustment) using Cohen's (1988) cut-offs: <0.20 = trivial; $0.20-0.50$ = small; $0.50-0.80$ = moderate; and ≥ 0.80 = large. Correlation between outcomes will employ Pearson and/or Spearman correlations at individual time points.

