Appendix VIII
Uniscale

Please circle the number (0-10) best reflecting your response to the following that describes your feelings **during the past week, including today.**

1. **How would you describe your overall Quality of Life?**

0	1	2	3	4	5	6	7	8	9	10
As bad as										As good as
it can be										it can be

**If you have not started treatment on this study,
please stop here. Thank you for taking the
time to help us.**

**If you have started treatment on this study,
please continue to the next page.**

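### The Skindex-16 directions in Appendix VI give a response range of 0-6, but the form's 16 items and Section 16.34 use 0-10

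*Combined protocol and SAP*

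**What the plan says.** The documents state the Skindex-16 response range in three places.

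- **Appendix VI, directions to the patient:** "Please circle the number (0-6) best reflecting your response".
- **Appendix VI, the items:** each of the 16 prints the row "0 1 2 3 4 5 6 7 8 9 10", with the never-bothered anchor at the low end and the always-bothered anchor at the high end.
- **Section 16.34:** "The Skindex-16 contains 16 questions each on a 0-10 scale (0=never bothered, 10=always bothered".

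On scoring, Section 16.34 says only that "each PRO will be scored according to the published scoring algorithm". It gives no rule for answers made under conflicting directions.

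The questionnaires are given at baseline and every cycle. The planned use is graphical ("Scale score trajectories over time will be examined using stream plots and mean plots with standard deviation error bars overall") and inferential ("Changes from baseline at each cycle will be statistically tested using paired t-tests"). Standardized response means are then read against fixed cut-offs of 0.20, 0.50 and 0.80.

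The goal served is "2.33 To describe patient-reported health-related quality of life and symptoms", which is listed with the translational and correlative goals.

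**The concern.** The range that disagrees with the other two is the one addressed to the patient. Someone who obeys it loses the top four options, including the anchor at 10. Someone who goes by the printed row does not. The same state could then be recorded differently by two patients, or by one patient at two visits, and the analysis would read that difference as a difference in skin symptoms.

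At stake is how far the Skindex-16 means, the changes from baseline and the standardized response means can be interpreted. Skin effects matter for this drug: Section 15.17 lists rash and dry skin among the effects reported in more than 10% of patients. Answers lost at the top of the scale cannot be recovered later.

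**Working it through.** No sample size, power or alpha is attached to Skindex-16, so there is no planned figure to reproduce. The check is a comparison of texts followed by arithmetic on the score range.

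**1. Is the conflict in the form itself?** The 0-10 row appears under all 16 items and agrees with Section 16.34. The Uniscale form in Appendix VIII opens with almost the same sentence and the matching range: "Please circle the number (0-10) best reflecting your response". The mismatch is therefore specific to the Skindex-16 directions and is not a fault of text extraction.

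**2. Range lost if the directions are followed literally.**

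| Quantity | Printed scale (0-10) | Directions (0-6) |
|---|---|---|
| Options per item | 11 | 7 (options 7, 8, 9 and 10 excluded) |
| Item maximum | 10 | 6 |
| Raw sum maximum, 16 items | 16 × 10 = 160 | 16 × 6 = 96 |
| Share of range | 100% | 96/160 = 60% |

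**3. Two ways of obeying the directions.** They have different effects.

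- *Truncation.* The patient keeps the 0-10 meaning but stops at 6, so the recorded value is min(x, 6). A move from 2 to 9 is recorded as 2 to 6, a change of 4 instead of 7. Where no answer would exceed 6, the effect is zero.
- *Rescaling.* The patient treats 6 as the top. The recorded value is 6/10 of the intended one, an understatement by a factor of 10/6 = 1.67. A circled 3 is 3/6 = 50% of a 0-6 scale but is scored as 3/10 = 30%.

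**4. Effect on the planned statistics.** Write d for the change from baseline.

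- If every patient rescales at every visit, each change becomes 0.6d. The mean and SD of change both shrink by 0.6, so (0.6 × mean d)/(0.6 × SD d) = mean d/SD d. The paired t statistic and the standardized response mean, before the adjustment that Section 16.34 names, do not change. Only the raw means do.
- If use is mixed between patients, two people who both go from never to always bothered record changes of 6 and 10. The form alone creates that spread, and it enters the SD of change.
- If use is mixed across visits, a patient midway up the scale both times could circle 0.5 × 10 = 5 at one visit and 0.5 × 6 = 3 at another. That is an apparent change of 2 points with no change in state.

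Distortion of the t-tests and standardized response means therefore needs truncation or mixed use. The documents give no figure for how often either would occur, so the affected share may lie anywhere from 0 to 100%.

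**The case against.** The strongest reply is that patients answer on the scale in front of them. The 0-10 row is printed 16 times with its anchors, the 0-6 range appears once in parentheses, and nothing stops anyone circling 7 to 10. Many patients may never act on the wrong range, and zero effect is possible. This stands. It limits the claim to what may happen but does not remove the contradiction.

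The issued form is also not in evidence. The test schedule and Section 18.1 require the patient questionnaire booklet and refuse copies, and that booklet is not among the documents. It may already be correct. This stands too, so the booklet has to be checked before it is corrected.

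A reader might infer three stronger things that the documents do not support:

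- *That patients cannot report severe skin problems.* This holds only for those who disregard the printed options 7 to 10. The items also ask how often the patient is bothered, so the top of the scale is frequency, not severity.
- *That the results are biased, or understated by 1.67.* The factor applies only to a patient who overrides the printed anchor at 10, and uniform rescaling leaves the test statistics as they were.
- *That dose modification for rash is affected.* Section 8.2 acts on CTCAE-graded maculo-papular rash, which Section 10.6 has graded at baseline and each evaluation. No rule uses Skindex-16.

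**Conclusion.** The inconsistency is real and stands in the current text of a patient-facing form. For a patient who follows the directions literally, the cap is exact: 6 instead of 10 per item, and 96 instead of 160 in the raw sum. The effect on mean changes and standardized response means is conditional and of unknown size. It requires some truncation, or some mixing of the two ranges across patients or visits, and it assumes that the issued booklet carries the Appendix VI wording.

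The reach is limited to one instrument under a descriptive, correlative goal. The clinical benefit rate, the two-stage rule in Section 16.21, the secondary endpoints in Section 16.32 and the adverse event stopping rule in Section 16.42 do not use it. The point deserves correction because the correction is cheap and the lost answers are not recoverable. It does not threaten the trial's conclusions on efficacy or safety.

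**What to change.** 1. In the Appendix VI directions, change (0-6) to (0-10), so that they agree with the items and with Section 16.34.
2. Check the wording of the patient questionnaire booklet actually issued, and correct it if it repeats the error.
3. If booklets with the old wording have been completed, record the booklet version for each visit and report the matter descriptively as a limitation of the Skindex-16 results. With at most 30 patients, a split by version would be too small to support more than description.

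Before first use, the cost is one number and, if needed, a reprint. Once the study is running there is a further cost: a mid-study change can put a patient's baseline and follow-up on different versions, and the paired changes would then span both. That is why the version has to be recorded by visit and not only by patient.

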Appendix VII Bowel Function Questionnaire

Directions: Each of the statements or questions below describe symptoms or problems which sometimes occur in patients with your type of cancer. Questions 2-10 can be answered by circling “yes” or “no”.

1. How many bowel movements do you have each day on average? _____
2. Do you sometimes have to get up at night to have a bowel movement? yes no
3. Do you sometimes lose control of your bowel movements? yes no
4. Do you sometimes have another bowel movement within 30 min of the previous one? yes no
5. Do you sometimes wear protective clothing or a pad in case you lose control of a bowel movement? yes no
6. Are you sometimes unable to tell the difference between stool and gas? yes no
7. Are your bowel movements sometimes liquid in consistency? yes no
8. Once you feel the urge to have a bowel movement, do you find that you must do so within 15 min to avoid an accident? yes no
9. Do you ever have cramping with bowel movements? yes no
 - If yes, is your cramping:**
 - mild
 - moderate
 - severe
10. Do you ever have blood in your bowel movement? yes no
 - If yes, check the description that best describes the amount of blood in your bowel movement:**
 - on toilet tissue only
 - mixed with or coating bowel movement
 - enough to turn water in toilet bowl red

Appendix VIII
Uniscale

Please circle the number (0-10) best reflecting your response to the following that describes your feelings **during the past week, including today.**

1. **How would you describe your overall Quality of Life?**

0	1	2	3	4	5	6	7	8	9	10
As bad as										As good as
it can be										it can be

**If you have not started treatment on this study,
please stop here. Thank you for taking the
time to help us.**

**If you have started treatment on this study,
please continue to the next page.**

Appendix X
Child-Pugh Classification

Parameter	Points Assigned		
	1	2	3
Ascites	Absent	Slight	Moderate
Bilirubin (mg/dL)	≤2	2 to 3	>3
Albumin (g/dL)	>3.5	2.8 to 3.5	<2.8
Prothombin Time			
Seconds over control	1 to 3	4 to 6	>6
INR	<1.7	1.8 to 2.3	>2.3
Encephalopathy	None	Grade 1 to 2	Grade 3 to 4

Modified Child-Pugh Classification of the severity of liver disease according to the degree of ascites, the plasma concentrations of bilirubin and albumin, the Prothrombin time, and the degree of encephalopathy. A total score of 5 to 6 is considered Grade A (well-compensated disease); 7-9 is Grade B (significant functional compromise); and 10 to 15 is Grade C (decompensated disease). These grades correlate with one and two year survival; Grade A – 100% and 65%; Grade B: 80% and 60%; and Grade C – 45% and 35%.

Appendix XI: MEDICATION GUIDE Iclusig[®] (eye-CLUE-sig) (ponatinib) Tablets**What is the most important information I should know about Iclusig?****Iclusig can cause serious side effects, including:**

Blood clots or blockage in your blood vessels (arteries and veins). Blood clots or blockage in your blood vessels may lead to heart attack, stroke, or death. A blood clot or blockage in your blood vessels can prevent proper blood flow to your heart, brain, bowels (intestines), legs, eyes, and other parts of your body. You may need emergency surgery or treatment in a hospital. Get medical help right away if you get any of the following symptoms:

- chest pain or pressure
- pain in your arms, legs, back, neck or jaw
- shortness of breath
- numbness or weakness on one side of your body
- trouble talking
- headache
- dizziness
- severe stomach area pain
- decreased vision or loss of vision

Blood clots or blockage in your blood vessels can happen in people with or without risk factors for heart and blood vessel disease, including people 50 years of age or younger. Talk to your healthcare provider if this is a concern for you.

Heart problems. Iclusig can cause heart problems, including heart failure which can be serious and may lead to death. Heart failure means your heart does not pump blood well enough. Iclusig can also cause irregular slow or fast heartbeats and heart attack. Your healthcare provider will check your heart function before and during your treatment with Iclusig. Get medical help right away if you get any of the following symptoms: shortness of breath, chest pain, fast or irregular heartbeats, dizziness, or feel faint.

Liver problems. Iclusig can cause liver problems, including liver failure, which can be severe and may lead to death. Your healthcare provider will do blood tests before and during your treatment with Iclusig to check for liver problems. Get medical help right away if you get any of these symptoms of liver problems during treatment:

- yellowing of your skin or the white part of your eyes (jaundice)
- dark “tea-colored” urine
- sleepiness

See “**What are the possible side effects of Iclusig?**” for information about side effects.

What is Iclusig?

Iclusig is a prescription medicine used to treat adults who have:

- a specific type of abnormal gene (T315I-positive) chronic phase, accelerated phase, or blast phase chronic myeloid leukemia (CML), or T315I-positive Philadelphia chromosome positive acute lymphoblastic leukemia (Ph+ ALL)
- chronic phase, accelerated phase, or blast phase CML or Ph+ ALL who cannot receive any other tyrosine kinase inhibitor (TKI) medicines

It is not known if Iclusig is safe and effective in children less than 18 years of age.

What should I tell my healthcare provider before taking Iclusig? Before you take Iclusig, tell your healthcare provider if you:

- have a history of blood clots in your blood vessels (arteries or veins)
- have heart problems, including heart failure, irregular heartbeats, and QT prolongation
- have diabetes
- have a history of high cholesterol
- have liver problems
- have had inflammation of your pancreas (pancreatitis)

have high blood pressure

- have bleeding problems
- plan to have any surgical procedures
- are lactose (milk sugar) intolerant. Iclusig tablets contain lactose.
- drink grapefruit juice
- have any other medical conditions
- are pregnant or plan to become pregnant. Iclusig can harm your unborn baby. You should not become pregnant while taking Iclusig. Tell your healthcare provider right away if you become pregnant or plan to become pregnant.
- are breastfeeding or plan to breastfeed. It is not known if Iclusig passes into your breast milk. You and your healthcare provider should decide if you will take Iclusig or breastfeed. You should not do both.

Tell your healthcare provider about all the medicines you take, including prescription medicines and over-the-counter medicines, vitamins, and herbal supplements. Iclusig and other medicines may affect each other causing side effects.

Know the medicines you take. Keep a list of them to show your healthcare provider and pharmacist when you get a new medicine.

How should I take Iclusig?

- Take Iclusig exactly as your healthcare provider tells you to take it.
- Your healthcare provider may change your dose of Iclusig or tell you to stop taking Iclusig.
- Do not change your dose or stop taking Iclusig without talking to your healthcare provider.
- Swallow Iclusig tablets whole. Do not crush or dissolve Iclusig tablets.
- You may take Iclusig with or without food.
- If you miss a dose of Iclusig, take your next dose at your regular time. Do not take 2 doses at the same time to make up for a missed dose.
- If you take too much Iclusig, call your healthcare provider or go to the nearest hospital emergency room right away.

What are the possible side effects of Iclusig? Iclusig may cause serious side effects, including:

See “**What is the most important information I should know about Iclusig?**”

- **High blood pressure.** Your blood pressure should be checked regularly and any high blood pressure should be treated while you are taking Iclusig. Tell your healthcare provider if you get headaches, dizziness, chest pain or shortness of breath.
- **Inflammation of the pancreas (pancreatitis).** Symptoms include sudden stomach-area pain, nausea, and vomiting. Your healthcare provider should do blood tests to check for pancreatitis during treatment with Iclusig.
- **Neuropathy.** Iclusig may cause damage to the nerves in your arms, brain, hands, legs, or feet (Neuropathy). Tell your healthcare provider if you get any of these symptoms during treatment with Iclusig:
 - muscle weakness, tingling, burning, pain, and loss of feeling in your hands and feet
 - double vision and other problems with eye sight, trouble moving the eye, drooping of part of the face, sagging or drooping eyelids
- **Effects on the eye.** Serious eye problems that can lead to blindness or blurred vision may happen with Iclusig. Tell your healthcare provider if you get any of the following symptoms: perceived flashes of light, light sensitivity, floaters, dry or itchy eyes, and eye pain. Your healthcare provider will monitor your vision before and during your treatment with Iclusig.
- **Severe bleeding.** Iclusig can cause bleeding which can be serious and may lead to death. Tell your healthcare provider if you get any signs of bleeding while taking Iclusig including:
 - vomiting blood or if your vomit looks like coffee-grounds

- o pink or brown urine
- o red or black (looks like tar) stools
- o coughing up blood or blood clots
- o unusual bleeding or bruising of your skin
- o menstrual bleeding that is heavier than normal
- o unusual vaginal bleeding
- o nose bleeds that happen often
- o drowsiness or difficulty being awakened
- o confusion
- o headache
- o change in speech
- **Fluid retention.** Your body may hold too much fluid (fluid retention). Tell your healthcare provider right away if you get any of these symptoms during treatment with Iclusig:
 - o swelling of your hands, ankles, feet, face, or all over your body
 - o weight gain
 - o shortness of breath and cough
- **Low blood cell counts.** Iclusig may cause low blood cell counts. Your healthcare provider will check your blood counts regularly during treatment with Iclusig. Tell your healthcare provider right away if you have a fever or any signs of an infection while taking Iclusig.
- **Tumor Lysis Syndrome (TLS).** TLS is caused by a fast breakdown of cancer cells. TLS can cause you to have:
 - o kidney failure and the need for dialysis treatment
 - o an abnormal heartbeat Your healthcare provider may do blood tests to check for TLS.
 - **Possible wound healing problems.** If you need to have a surgical procedure, tell your healthcare provider that you are taking Iclusig. You should stop taking Iclusig at least 1 week before any planned surgery.
 - **A tear in your stomach or intestinal wall (perforation).** Tell your healthcare provider right away if you get:
 - o severe pain in your stomach-area (abdomen)
 - o swelling of the abdomen
 - o high fever

The most common side effects of Iclusig include:

- skin rash
- constipation
- stomach-area (abdomen) pain
- fever
- tiredness
- joint pain
- headache
- nausea
- dry skin

Tell your healthcare provider if you have any side effect that bothers you or that does not go away.

These are not all of the possible side effects of Iclusig. For more information, ask your healthcare provider or pharmacist.

Call your doctor for medical advice about side effects. You may report side effects to FDA at [REDACTED]

How should I store Iclusig?

Store Iclusig at room temperature between 68°F to 77°F (20°C to 25°C).

Keep Iclusig and all medicines out of the reach of children.

General information about Iclusig

Medicines are sometimes prescribed for purposes other than those listed in a Medication Guide. Do not use Iclusig for a condition for which it was not prescribed. Do not give Iclusig to other people, even if they have the same symptoms you have. It may harm them.

You can ask your healthcare provider or pharmacist for information about Iclusig that is written for health professionals.

For more information, go to www.iclusig.com or call [REDACTED]

What are the ingredients in Iclusig?

Active ingredient: ponatinib

Inactive ingredients: lactose monohydrate, microcrystalline cellulose, sodium starch glycolate (type B), colloidal silicon dioxide and magnesium stearate. The tablet coating consists of talc, polyethylene glycol, polyvinyl alcohol and titanium dioxide.

This Medication Guide has been approved by the U.S. Food and Drug Administration.

Manufactured for: ARIAD Pharmaceuticals, Inc. [name]

Revised: December 2013

Reference ID: 3425782

